Study Type	Project 4 Testing preliminary efficacy of a program to reduce barriers to community participation. Translational Trial Phase I Allocation: Randomized Intervention model: Parallel Assignment Primary purpose: Community reintegration
Date of First Enrollment	November 3, 2020
Target Sample Size	50
Recruitment Status	Project 4, closed to recruitment
Primary Outcome(s)	
Project 4 Testing Preliminary Efficacy of a Program to Reduce Barriers to Community Participation: We will test the working hypothesis that an adapted program, focused on resolving environmental barriers and building self-management skills in the home and community, will be feasible and superior to usual care for daily activity performance and participation outcomes. The hypothesis is based on our previous work,^{2,3} the work of others,⁴⁻⁶ and our unpublished preliminary data.
 
Aim 1. Determine the acceptability and feasibility of the adapted program. We will conduct a process evaluation⁷ of this intervention to evaluate the acceptability and feasibility and to aid in the interpretability of the trial. We will test the hypothesis that the adapted program will have high acceptability (80% retention), high fidelity by therapists (95% of elements and 90% of dose delivered), low safety risk (no increased rate of falls or health care use compared with control group), and high adherence (80% of modifications in use) at 6 months.
 
Aim 2. Estimate the magnitude of efficacy of the adapted program on the primary outcome of community participation (RNL) and on exploratory outcomes of daily activity performance and self-efficacy (I-HOPE) to select optimal end points for a large pragmatic trial. We will test the hypotheses that the adapted program is superior to usual care at 6 months on the primary and secondary end points.
 
Time Points of Interest: Baseline, 1 month

ORGANIZATIONAL STRUCTURE AND RESPONSIBILITIES

Principal Investigator:

[name], OTR/L

Responsibilities include: Managing the operations of the study, ensuring tasks are completed, ensuring compliance with quality-assurance requirements (e.g., human participant protection), preparing interim reports, and publication of study reports.

Study Coordinators:

[name], MSOT, OTR/L and [name], OTD, OTR/L

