We will conduct a trial to reduce the “science to service” gap using the CBRN.^{70,71} Hybrid designs examine efficacy while conducting a process evaluation of an intervention.⁷² We anticipate that a hybrid approach will lead to more rapid translational gains in intervention uptake, more effective implementation strategies, and more useful information for decision makers. We will facilitate translation by “designing for implementation and dissemination”⁷³ to ensure that findings are useful, relevant, and ready for widespread dissemination.⁷⁴ We will use the RE-AIM framework⁶⁷ (Figure 2) to adapt the intervention, to design the trial, and to plan for potential future dissemination through the CBRN.⁷⁵ Cost is an important factor that influences decisions and uptake of interventions.⁷⁶ To evaluate potential for implementation, we will examine costs to deliver the intervention, with engagement of CBRN members. This approach will provide CBOs with a better understanding of the impact of an intervention and incorporate RE-AIM metrics to aid in understanding the translation and sustainability of the program.

[figure not shown]

Figure 2. RE-AIM framework used to adapt the program

Study Participants

Recruitment

The eligibility criteria include (1) age 45-65 years; (2) self-report of difficulty with ≥ 2 daily activities using the OARS ADL scale⁸¹; and (3) onset of a physical disability 5 years prior to participation (eg, SCI, cerebral palsy, post-polio syndrome, stroke, amputation). We will exclude those currently institutionalized.

To ensure that the sample represents people that this program will target in the future (reach),⁸² we will select a sample of 50 adults aging with a long-term disability from the St. Louis members of the CBRN or who have participated in our previous cohort study of PAwLTPD. The CBRN offers access to PAwLTPD who are hard to reach in the traditional health care system and who could benefit from the intervention. In the current cohort of SLAAA participants, 2526 are aged 45-65 years (people with disabilities). Paraquad serves 420 people with physical disabilities aged 45-65 years who meet the eligibility criteria. We will invite eligible participants to participate by telephone. All recruitment and study materials will be IRB approved.

Randomization and Blinding

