The new program will be iteratively piloted with 3-6 individuals living with a long-term physical disability. The pilot participants will identify potential problems with acceptability of the program structure or process and information delivered to the participant. The program will be iteratively revised until a final program is sufficiently ready to deploy in a larger sample.

Outcomes will be assessed by blinded evaluators at baseline and 6 months. Our goal is to optimize the design of future trials, so we will examine a series of measures to evaluate their utility in the trial setting. Baseline and 6-month follow-up assessments will be conducted in the home by a trained and certified rater blinded to group allocation. Follow-up assessments will be completed by a blinded rater who did not conduct the T1 evaluation, as new home modifications could reveal group assignment. We will also track falls on a monthly basis.

Assessments

Primary Outcomes

In-Home Occupational Performance Evaluation (I-HOPE): The I-HOPE will be used to measure current activity patterns of participants, identify activities that are difficult but important to them, and identify the environmental barriers that influence those activities (person-environment fit). The I-HOPE is a multi-step assessment that evaluates the performance of people doing 42 activities in the home. Using labeled pictures of each home activity (e.g., washing dishes, getting in and out of bed), participants identify and prioritize preferred activities for intervention and give a subjective performance, satisfaction, and self-efficacy score for each activity. A trained rater (e.g., OT) observes the participant perform the activity and quantifies the person-environment fit (or misfit). The instrument yields five subscales- the activity subscale [$\alpha = 0.78$ (6 items)]; performance subscale [$\alpha = 0.85$ (8 items)]; satisfaction subscale [$\alpha = 0.77$ (8 items)]; self-efficacy subscale [$\alpha = 0.90$ (10 items)]; and the environmental barrier subscale [$\alpha = 0.77$ (6 items)]. Intraclass correlation coefficients were calculated for the I-HOPE subscales on a sample of 10 participants, and scores ranged from .94 to 1.0 for raters.¹⁴¹

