The goal of Aim 2 is to test the hypothesis that the adapted program will result in greater improvements in participation and daily activity performance than control at 6 months after intervention. Mixed-model repeated-measures analysis of variance will be used for longitudinal analyses of variables measured at >2 time points (ie, Reintegration to Normal Living Index, I-HOPE). The focus of this analysis will be the significance of the interaction between group and time. Hypotheses will test for interactions in terms of the equality of changes over time in the 2 groups. Contrasts will be used in testing the null hypothesis that changes between 2 specific time points in one group are equal to corresponding changes in the group. I-HOPE scores will be analyzed with analysis of covariance with the 6-month value as the dependent variable and the baseline value as the covariate. For all analyses, we will determine whether required distributional and model-specific assumptions are satisfied. To explore the potential trial end points, we will select the best independent indicator of participation and compare the measures for sensitivity and statistical efficiency with data collected at 6 months after intervention.

Sample Size Calculations

Although statistical significance is not the goal of this study, we estimated a sample size using a power analysis for a 2-sided, 2-sample, unequal-variance *t* test using G*Power with a significance level of 5% and power of 80%.¹⁷³ The sample size calculation includes a correlation between baseline and follow-up measures and is based on analysis of change scores, which is equivalent in efficiency to the proposed analytic model. Data were used from a pilot study with a total of 113 community-dwelling older adults.¹⁰⁰ We estimated the sample size for the mechanism of action (reducing environmental barriers). Environmental barrier mean changes in intervention and control groups were 26.28 (SD 18.03) and 10.09 (SD 22.27), respectively. A sample size of 50 (25 in each group) is needed to provide 80% power.

Potential Benefits, Risks and Alternatives

Benefits

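### The stated 80% power assumes that essentially all 50 enrolled participants give 6-month data; no attrition allowance is made, and power is about 69% at 80% retention in both groups (minor)

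*Combined protocol and SAP*

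**What the plan says.** The Sample Size Calculations section describes a power analysis for a two-sided, two-sample, unequal-variance t test at the 5% level with 80% power. It says of its basis: "The sample size calculation includes a correlation between baseline and follow-up measures and is based on analysis of change scores". The outcome is not the primary one: "We estimated the sample size for the mechanism of action (reducing environmental barriers"). The pilot inputs are mean changes of 26.28 (SD 18.03) in the intervention group and 10.09 (SD 22.27) in the control group. The conclusion is "A sample size of 50 (25 in each group) is needed to provide 80% power".

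The Recruitment section uses the same number for enrolment: "we will select a sample of 50 adults aging with a long-term disability". The summary table at the front also gives a target sample size of 50. No section states a dropout rate or an inflation for loss, or says whether 50 means enrolled or evaluable participants.

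Aim 1 sets a benchmark for feasibility: "the adapted program will have high acceptability (80% retention"), judged at 6 months. The sample-size section opens with a qualification: "Although statistical significance is not the goal of this study".

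**The concern.** Outcomes are taken at baseline and 6 months, so a change score needs a completed 6-month assessment. If 50 are enrolled and 50 are needed for 80% power, any loss takes the trial below the stated figure. Aim 1 would count the loss of one participant in five as high acceptability. The trial could therefore succeed on its own retention criterion and still not have the power it states, and the text does not tell the reader so.

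What is at stake is interpretation. The trial is meant to inform a larger pragmatic trial, and Aim 2 states superiority hypotheses. A reader who takes 80% at face value may give a non-significant result more weight than it deserves. The figure also concerns environmental barriers. It does not carry over to RNL, which Aim 2 names as the primary outcome and for which no power is given.

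**Working it through.** **Inputs**, all from Sample Size Calculations: difference 26.28 − 10.09 = 16.19; SDs of change s1 = 18.03 (intervention) and s2 = 22.27 (control); two-sided alpha 0.05. Allocation is 1:1 (Randomization and Blinding). Retention of 80% is the Aim 1 benchmark, and 0.8 × 25 = 20 per group.

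**Reproducing the plan's figure.** The root-mean-square SD is √[(18.03² + 22.27²)/2] = √[(325.08 + 495.95)/2] = 20.26, so d = 16.19/20.26 = 0.799. By the normal approximation, n per group = 2(1.960 + 0.842)²/0.799² ≈ 24.6, which rounds up to 25. Power at 25 per group is then 80.7%. The stated 50 is reproduced.

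**The test the plan names.** For group sizes n1 and n2:

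- SE = √(s1²/n1 + s2²/n2)
- df = (s1²/n1 + s2²/n2)² / [(s1²/n1)²/(n1 − 1) + (s2²/n2)²/(n2 − 1)]
- noncentrality = 16.19/SE
- power = probability that a noncentral t variable with these values falls outside ± the 97.5% point of t on df

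| Intervention / control with 6-month data | SE | df | Noncentrality | Power |
|---|---|---|---|---|
| 25 / 25 (all followed) | 5.731 | 46.0 | 2.825 | 79.0% |
| 20 / 25 (80% in intervention group only) | 6.008 | 43.0 | 2.695 | 75.0% |
| 20 / 20 (80% in both groups) | 6.407 | 36.4 | 2.527 | 69.1% |

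Simulation with 200,000 runs gives 79.0% at 25/25 and 69.0% at 20/20.

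**Uneven loss.** Four other splits of 40 evaluable participants give 69.7% (18/22), 67.5% (22/18), 68.5% (15/25) and 63.0% (25/15). The last is lowest because the smaller group is then the one with the larger SD.

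The rows for 20/25 and 20/20 correspond to two readings of the benchmark. Aim 1 attaches it to the adapted program, while the process evaluation (Reach, and Table 4) tracks retention without naming a group.

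**The case against.** **This is a pilot and significance is not its goal.** This is the strongest objection, and it stands as to weight. The plan disclaims significance, Aim 2 is framed first as estimating magnitude and selecting end points, and recruitment is closed. Once results exist, observed retention and confidence intervals will say more than hypothetical power. Still, the plan prints a power figure and states superiority hypotheses, so it should say when that figure holds.

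**79% against 80%.** A reader might infer an arithmetic error from the 79.0% at full follow-up. The documents do not support that: 25 per group is the normal-approximation answer, and the gap is one of method and rounding.

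**The plan expects to lose 20%.** A reader might infer this too. The 80% is a threshold for judging acceptability, and no section forecasts dropout. The 69% is conditional on retention only just meeting the threshold in both groups.

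**Baseline adjustment would restore the power.** The Statistical Analyses section says: "I-HOPE scores will be analyzed with analysis of covariance with the 6-month value as the dependent variable". The Assessments section lists, among the I-HOPE scales, "and the environmental barrier subscale". If that subscale is the sizing outcome, which the plan does not say, adjustment could help. With the cost of baseline imbalance included and equal baseline and follow-up SDs assumed, power at 20 per group is about 70%, 75%, 80% and 85% for assumed correlations of 0.9, 0.7, 0.5 and 0.3. The plan gives no correlation beyond what its SDs of change already contain. Its sample-size section also treats change scores as no less efficient than the planned model, so it claims no such reserve itself. The objection shows that power could be higher, not that the printed 80% allows for loss.

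**Conclusion.** The point holds as a minor one. The stated 80% power for change in environmental barriers is correct to rounding for 50 participants with complete 6-month data. It is not correct for 50 enrolled with appreciable loss. On the same test it is about 75% at 20 against 25, and about 69% at 20 against 20, with 63% to 70% across the uneven splits of 40 that were checked.

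These figures assume the pilot means and SDs of change, analysis of participants with both assessments, and loss unrelated to outcome. They do not apply to RNL.

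A reader might go further and infer that the trial is too small or should have enrolled more. The documents do not support that for a feasibility pilot that disclaims significance as its goal. What is missing is the condition under which the stated power holds.

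**What to change.** Keep 50 and keep the analysis. Replace the last sentence of Sample Size Calculations with:

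> Fifty participants (25 per group) give about 80% power for change in environmental barriers if all complete the 6-month assessment. No allowance is made for attrition; on the same change-score t test, power is about 69% with 20 evaluable per group (80% retention in both groups). The trial is not sized for RNL.

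Do not add a claim of gain from baseline adjustment to this text as it stands, because it would contradict the retained statement in the same paragraph that change scores match the planned model in efficiency. If such a gain is to be claimed, revise that statement first, state the correlation assumed, and use values that include the cost of baseline imbalance (about 70% to 85% at 20 per group for assumed correlations of 0.9 to 0.3, with equal baseline and follow-up SDs).

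The cost is wording only, with no added participants and no change of method. The one downside is that the stated power looks less favourable.
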